#### **14.4. Confidentiality**

Celgene affirms the subject's right to protection against invasion of privacy and to be in compliance with ICH and other local regulations (whichever is most stringent). Celgene requires the Investigator to permit Celgene's representatives and, when necessary, representatives from regulatory authorities, to review and/or copy any medical records relevant to the study in accordance with local laws.

Should direct access to medical records require a waiver or authorization separate from the subject's signed informed consent document, it is the responsibility of the Investigator to obtain such permission in writing from the appropriate individual.

#### **14.5. Protocol Amendments**

Any amendment to this protocol must be approved by the Celgene Clinical Research Physician/Medical Monitor. Amendments will be submitted to the IRB/EC for written approval. Written approval must be obtained before implementation of the amended version occurs. The written signed approval from the IRB/EC should specifically reference the Investigator name, protocol number, study title and amendment number(s) that is applicable. Amendments that are administrative in nature do not require IRB/IEC approval but will be submitted to the IRB/IEC for information purposes.

#### **14.6. Institutional Review Board/Independent Ethics Committee Review and Approval**

Before the start of the study, the study protocol, informed consent document, and any other appropriate documents will be submitted to the IRB/EC with a cover letter or a form listing the documents submitted, their dates of issue, and the site (or region or area of jurisdiction, as applicable) for which approval is sought. If applicable, the documents will also be submitted to the authorities in accordance with local legal requirements.

The IP can only be supplied to an Investigator by Celgene or its authorized representative after documentation on all ethical and legal requirements for starting the study has been received by Celgene or its authorized representative. This documentation must also include a list of the members of the IRB/EC and their occupation and qualifications. If the IRB/EC will not disclose the names, occupations and qualifications of the committee members, it should be asked to issue a statement confirming that the composition of the committee is in accordance with GCP. For example, the IRB General Assurance Number may be accepted as a substitute for this list. Formal approval by the IRB/EC should mention the protocol title, number, amendment number (if applicable), study site (or region or area of jurisdiction, as applicable), and any other documents reviewed. It must mention the date on which the decision was made and must be officially signed by a committee member. Before the first subject is enrolled in the study, all ethical and legal requirements must be met.

The IRB/EC and, if applicable, the authorities, must be informed of all subsequent protocol amendments in accordance with local legal requirements. Amendments must be evaluated to determine whether formal approval must be sought and whether the informed consent document should also be revised.

The Investigator must keep a record of all communication with the IRB/EC and, if applicable, between a Coordinating Investigator and the IRB/EC. This statement also applies to any communication between the Investigator (or Coordinating Investigator, if applicable) and regulatory authorities.

Any advertisements used to recruit subjects for the study must be reviewed by Celgene and the IRB/EC prior to use.

#### **14.7. Ongoing Information for Institutional Review Board / Ethics Committee**

If required by legislation or the IRB/EC, the Investigator must submit to the IRB/EC:

- Information on serious or unexpected adverse events as soon as possible;
- Periodic reports on the progress of the study;
- Deviations from the protocol or anything that may involve added risk to subjects.

#### **14.8. Closure of the Study**

Celgene reserves the right to terminate this study at any time for reasonable medical or administrative reasons. Any premature discontinuation will be appropriately documented according to local requirements (eg, IRB/EC, regulatory authorities, etc).

In addition, the Investigator or Celgene has the right to discontinue a single site at any time during the study for medical or administrative reasons such as:

- Unsatisfactory enrollment;
- GCP noncompliance;
- Inaccurate or incomplete data collection;
- Falsification of records;
- Failure to adhere to the study protocol.

## **15. DATA HANDLING AND RECORDKEEPING**

### **15.1. Data/Documents**

The Investigator must ensure that the records and documents pertaining to the conduct of the study and the distribution of the investigational product are complete, accurate, filed and retained. Examples of source documents include: hospital records; clinic and office charts; laboratory notes; memoranda; subject's diaries or evaluation checklists; dispensing records; recorded data from automated instruments; copies or transcriptions certified after verification as being accurate copies; microfiche; x-ray film and reports; and records kept at the pharmacy, and the laboratories, as well as copies of eCRFs or CD-ROM.

### **15.2. Data Management**

Data will be collected via eCRF and entered into the clinical database per Celgene SOPs. This data will be electronically verified through use of programmed edit checks specified by the clinical team. Discrepancies in the data will be brought to the attention of the clinical team, and investigational site personnel, if necessary. Resolutions to these issues will be reflected in the database. An audit trail within the system will track all changes made to the data.

### **15.3. Record Retention**

Essential documents must be retained by the Investigator for a minimum of 2 years after the last approval of a marketing application in an ICH region and until there are no pending or contemplated marketing applications in an ICH region, or at least 2 years have elapsed since the formal discontinuation of clinical development of the IP. The Investigator must retain these documents for the time period described above or according to local laws or requirements, whichever is longer. Essential documents include, but are not limited to, the following:

- Signed informed consent documents for all subjects;
- Subject identification code list, screening log (if applicable), and enrollment log;
- Record of all communications between the Investigator and the IRB/EC;
- Composition of the IRB/EC;
- Record of all communications between the Investigator, Celgene, and their authorized representative(s);
- List of Sub-Investigators and other appropriately qualified persons to whom the Investigator has delegated significant study-related duties, together with their roles in the study, curriculum vitae, and their signatures;
- Copies of eCRFs (if paper) and of documentation of corrections for all subjects;
- IP accountability records (see Section 8.5);
- Record of any body fluids or tissue samples retained;

- All other source documents (subject records, hospital records, laboratory records, etc):
- All other documents as listed in Section 8 of the ICH consolidated guideline on GCP (Essential Documents for the Conduct of a Clinical Trial).

The Investigator must notify Celgene if he/she wishes to assign the essential documents to someone else, remove them to another location or is unable to retain them for a specified period. The Investigator must obtain approval in writing from Celgene prior to destruction of any records. If the Investigator is unable to meet this obligation, the Investigator must ask Celgene for permission to make alternative arrangements. Details of these arrangements should be documented.

All study documents should be made available if required by relevant health authorities. Investigator/Institution should take measures to prevent accidental or premature destruction of these documents.

## **16. QUALITY CONTROL AND QUALITY ASSURANCE**

All aspects of the study will be carefully monitored by Celgene or its authorized representative for compliance with applicable government regulations with respect to current GCP and standard operating procedures.

### **16.1. Study Monitoring and Source Data Verification**

Celgene ensures that appropriate monitoring procedures are performed before, during and after the study. Before the study is initiated at a site visit or at an Investigator meeting, all aspects of the study are reviewed with the Investigator and the staff. Prior to enrolling subjects into the study, a Celgene representative will review the protocol, eCRFs, procedures for obtaining informed consent, record keeping, and reporting of AEs/SAEs with the Investigator. Monitoring will include on-site visits with the Investigator and his/her staff as well as any appropriate communications by mail, email, fax, or telephone. At each monitoring visit, the facilities, investigational product storage area, eCRFs, subject's source documents, and all other study documentation will be inspected/reviewed by the Celgene representative for accuracy, adherence to the protocol and Good Clinical Practice.

Accuracy will be checked by performing source data verification that is a direct comparison of the entries made onto the eCRFs against the appropriate source documentation. Any resulting discrepancies will be reviewed with the Investigator and/or his/her staff. Any necessary corrections will be made directly to the eCRFs or via queries by the Investigator and/or his/her staff. Monitoring procedures require that informed consents, adherence to inclusion/exclusion criteria and documentation of SAEs and their proper recording be verified. Additional monitoring activities may be outlined in a study-specific monitoring plan.

### **16.2. Audits and Inspections**

In addition to the routine monitoring procedures, a Good Clinical Practice Quality Assurance unit exists within Celgene. Representatives of this unit will conduct audits of clinical research activities in accordance with Celgene and/or designee SOPs to evaluate compliance with Good Clinical Practice guidelines and regulations.

The Investigator is required to permit direct access to the facilities where the study took place, source documents, eCRFs and applicable supporting records of study subject participation for audits and inspections by IRB/IECs, regulatory authorities (eg, FDA, EMA, Health Canada) and company authorized representatives. The Investigator should make every effort to be available for the audits and/or inspections. If the Investigator is contacted by any regulatory authority regarding an inspection, he/she should contact Celgene immediately.

## **17. PUBLICATIONS**

The results of this study may be published in a medical publication, journal, or may be used for teaching purposes. Additionally, this study and its results may be submitted for inclusion in all appropriate health authority study registries, as well as publication on health authority study registry websites, as required by local health authority regulations. Selection of first authorship will be based on several considerations, including, but not limited to study participation, contribution to the protocol development, and analysis and input into the manuscript, related abstracts, and presentations in a study.

## **19. APPENDICES**

### **Appendix A: Wagner Grading Scale**

#### **Wagner Ulcer Classification System**

Grade 0: No open lesions; may have deformity or cellulitis

Grade 1: Superficial diabetic ulcer (partial or full-thickness)

Grade 2: Ulcer extension to ligament, tendon, joint capsule, or deep fascia without abscess or osteomyelitis

Grade 3: Deep ulcer with abscess, osteomyelitis, or joint sepsis

Grade 4: Gangrene localized to portion of forefoot or heel

Grade 5: Extensive gangrenous involvement of the entire foot

Source: [Frykberg, 2002](#).

## Appendix B: Rutherford Classification of Chronic Limb Ischemia

**Table A1: Rutherford Classification of Chronic Limb Ischemia**

Grade	Category	Clinical Description	Objective Criteria
0	0	Asymptomatic—no hemodynamically significant occlusive disease	Normal treadmill or reactive hyperemia test
	1	Mild claudication	Completes treadmill exercise a ; AP after exercise >50 mmHg but at least 20 mmHg lower than resting value
I	2	Moderate claudication	Between categories 1 and 3
	3	Severe claudication	Cannot complete standard treadmill exercise a and AP after exercise <50 mmHg
II b	4	Ischemic rest pain	Resting AP <40 mmHg, flat or barely pulsatile ankle or metatarsal PVR; TP <30 mmHg
III b	5	Minor tissue loss—nonhealing ulcer, focal gangrene with diffuse pedal ischemia	Resting AP <60 mmHg, ankle or metatarsal PVR flat or barely pulsatile; TP <40 mmHg
	6	Major tissue loss—extending above TM level, functional foot no longer salvageable	Same as Category 5

Abbreviations: AP = ankle pressure; PVR = pulse volume recording; TM = transmetatarsal; TP = toe pressure.

a Five minutes at 2 mph on a 12% incline.

b Grades II and III, categories 4, 5, and 6, are embraced by the term chronic critical ischemia.

Source: [Rutherford, 1997](#).

## Appendix C: New York Heart Association (NYHA) Classification

[figure not shown]
**Table A2: New York Heart Association Classification**

Class	Patient Symptoms
Class I (Mild)	No limitation of physical activity. Ordinary physical activity does not cause undue fatigue, palpitation, or dyspnea (shortness of breath).
Class II (Mild)	Slight limitation of physical activity. Comfortable at rest, but ordinary physical activity results in fatigue, palpitation, or dyspnea.
Class III (Moderate)	Marked limitation of physical activity. Comfortable at rest, but less than ordinary activity causes fatigue, palpitation, or dyspnea.
Class IV (Severe)	Unable to carry out any physical activity without discomfort. Symptoms of cardiac insufficiency at rest. If any physical activity is undertaken, discomfort is increased.

Source: [The Criteria Committee of the New York Heart Association](http://www.abouthf.org/questions_stages.htm) NYHA Classification – The stages of heart failure. Heart Failure Society of America. [http://www.abouthf.org/questions\\_stages.htm](http://www.abouthf.org/questions_stages.htm). Accessed 28 Sep 2012.

## Appendix D: Visual Analog Scale Pain

### Numeric Pain Scale

Source: [Johnson, 2005](#).

## Appendix E: E-Z Graph Wound Assessment

**E-Z GRAPH® WOUND ASSESSMENT WORKSHEET**

### CLASSIFICATIONS

**SUSPECTED DEEP TISSUE INJURY:** Purple or maroon localized area of discolored intact skin or blood-filled blister due to damage of underlying soft tissue from pressure and/or shear. The area may be preceeded by tissue that is painful, firm, mushy, boggy, warmer, or cooler as compared to adjacent tissue.

**STAGE I:** Intact skin with non-blanchable redness of a localized area usually over a bony prominence. Darkly pigmented skin may not have visible blanching; its color may differ from the surrounding area.

**STAGE II:** Partial thickness loss of dermis presenting as a shallow open ulcer with a red pink wound bed, without slough. May also present as an intact or ruptured serum-filled blister.

**STAGE III:** Full thickness tissue loss. Subcutaneous fat may be visible but bone, tendon or muscle are not exposed. Slough may be present but does not obscure the depth of tissue loss. May include undermining and tunneling.

**STAGE IV:** Full thickness skin loss with exposed bone, tendon or muscle. Slough or eschar may be present on some parts of the wound bed. Often include undermining and tunneling.

**NOT STAGEABLE:** Full thickness tissue loss in which the base of the ulcer is covered by slough (yellow, tan, gray, green or brown) and/or eschar (tan, brown, black) in the wound bed.

### E-Z GRAPH® WOUND ASSESSMENT SYSTEM

NAME \_\_\_\_\_ DATE \_\_\_\_\_

WOUND LOCATION \_\_\_\_\_

TX BEING USED \_\_\_\_\_

STAGE: 1 2 3 4 Not Stageable Deep Tissue Injury Partial thickness Full thickness

LENGTH \_\_\_\_\_ cm WIDTH \_\_\_\_\_ cm DEPTH \_\_\_\_\_ cm ODOR \_\_\_\_\_ Y N

WD BASE: Red Pink Yellow White Gray Brown Black Purple ESCHAR/SLOUGH Y N

DRAINAGE AMT: None Small Moderate Heavy UNDERMINING Y N

DRAINAGE TYPE: Serous Serous/Bloody Bloody Green Purulent TUNNELING Y N

PERIWOUND: Clean Moderated Erythematous Edematous Denuded Callosities High Scale White Brown Purple

ASSESSOR SIGNATURE: \_\_\_\_\_

CODE SYSTEM: 12 o'clock

BLUE - WOUND MARGINS  
RED - HYDROMA  
BLACK - ESCHAR  
ARROWS - DIRECTION

POSITIONING GRAPH  
CENTER DOT OF GRAPH  
OVER WOUND AREA TOP  
OF GRAPH TOWARD  
WOUND ENDS

RETAIN TOP COPY FOR RECORDS

DISCARD BACK AFTER USE

E-Z Graph distributed by  
E. Z. Graph of Victoria, Inc.  
Patent # 5265805 [name]

BEND AT CORNER TO PEEL OFF BACKING

CEMTRAC 100

Free back right - E-Z GRAPH®  
and apply noted above

DO NOT WRITE IN THIS AREA  
For facility use, with reading graph above

© 2000, 2007 E.Z. Graph of Victoria, Inc.  
All rights reserved.  
E.Z. Graph of Victoria, Inc.  
[contact] [name]  
[name]

## Appendix E: E-Z Graph Wound Assessment (Continued)

Indicate wound site on appropriate figure with "X".

FRONT BACK LEFT RIGHT

Right Left Right Dorsal Left Dorsal Right Palmar Left Palmar Right Dorsal Left Dorsal Right Plantar Left Plantar Right Medial Right Lateral Left Medial Left Lateral Right Anterior Left Anterior Right Posterior Left Posterior

Circle appropriate choices below. Signature \_\_\_\_\_ Date \_\_\_\_\_

**THIS WOUND IS** Present on Admission New Acquired Previously documented Arterial Venous  
 Diabetic or neuropathic Pressure Surgical Traumatic Undetermined at this time  
 Burn Other: \_\_\_\_\_

**AGE OF WOUND** Acute (duration less than 6 wks) Date occurred: \_\_\_\_\_  
 Chronic (duration greater than 6 wks) Date occurred: \_\_\_\_\_

**PAIN PRESENT** On touch Only when performing wound care All the time With weight bearing  
 Positional - with elevation when dependent No pain at all Other: \_\_\_\_\_

**WOUND STATUS** Improved Healed Unchanged Deteriorated Initial Assessment  
 \_\_\_\_\_ % epithelialized \_\_\_\_\_ % granulation \_\_\_\_\_ % clean, nongranulating \_\_\_\_\_ % slough \_\_\_\_\_ % eschar \_\_\_\_\_ % smaller in size

**NARRATIVE:** \_\_\_\_\_

[figure not shown]
**TREATMENT GOALS**

1. Pressure redistribution.
2. Improve nutrition.
3. Promote circulation.
4. Control or reduce bacterial colonization.
5. Decrease or remove necrotic tissue.
6. Promote comfort or decrease pain.
7. Decrease exudate / odor / odors.
8. Promote granulation / contraction / re-epithelialization.

## **Appendix F: Guidelines for Digital Images Documenting Ulcer Healing Over Time**

[figure not shown]

## **Appendix G: Thawing and Dilution Protocol**

[figure not shown]

## **Appendix G: Thawing and Dilution Protocol (Continued)**

## **Appendix G: Thawing and Dilution Protocol (Continued)**

## Appendix H: Canadian Cardiovascular Society Angina Grading Scale

Clinical Findings	Features	Grade
no limitation of ordinary activity	Ordinary physical activity (such as walking or climbing stairs) does not cause angina. Angina may occur with strenuous rapid or prolonged exertion at work or recreation.	I
slight limitation of ordinary activity.	Angina may occur with 
 
• walking or climbing stairs rapidly;
 
• walking uphill;
 
• walking or stair climbing after meals or in the cold in the wind or under emotional stress;
 
• walking more than 2 blocks on the level at a normal pace and in normal conditions
 
• climbing more than 1 flight of ordinary stairs at a normal pace and in normal conditions
 
	II
marked limitation of ordinary physical activity	Angina may occur after 
 
• walking 1-2 blocks on the level or
 
• climbing 1 flight of stairs in normal conditions at a normal pace
 
	III
unable to carry on any physical activity without discomfort	Angina may be present at rest.	IV

Source: [Campeau, 1976](#).

1. LIST OF ABBREVIATIONS

Table 1: Abbreviations and Specialist Terms

ABBREVIATION	MEANING
ABI	ANKLE-BRACHIAL INDEX
CEC	CIRCULATING ENDOTHELIAL CELL
CT	COMPUTED TOMOGRAPHY
DFU	DIABETIC FOOT ULCER
DLT	DOSE-LIMITING TOXICITY
DMC	DATA MONITORING COMMITTEE
ECG	ELECTROCARDIOGRAM
IM	INTRAMUSCULAR
IP	INVESTIGATIONAL PRODUCT
MRI	MAGNETIC RESONANCE IMAGING
MTD	MAXIMUM TOLERATED DOSE
PAD	PERIPHERAL ARTERIAL DISEASE
PBMC	PERIPHERAL BLOOD MONONUCLEAR CELLS
PCR	POLYMERASE CHAIN REACTION
PT	PROTHROMBIN TIME
PTT	PARTIAL THROMBOPLASTIN TIME

SD	STANDARD DEVIATION
TAT	THROMBIN ACTIVATION TIME
TBI	TOE BRACHIAL INDEX
TF-PCA	TISSUE FACTOR PROCOAGULANT ACTIVITY
VAS	VISUAL ANALOGUE SCALE
VEGF	VASCULAR ENDOTHELIAL GROWTH FACTOR

2. INTRODUCTION

This statistical analysis plan (SAP) describes the analyses and data presentations for Celgene's protocol CCT-PDA-002-DFU-001, "A Phase I, Multicenter, Open-label, Dose-escalation Study to Evaluate the Safety and Efficacy of Intramuscular Injection of Human Placenta-derived Cells (PDA-002) in subjects with Peripheral Arterial Disease and Diabetic Foot Ulcer, Amendment 3" which was issued on 6 February, 2014. It contains definitions of analysis populations, derived variables and statistical methods for the analysis of efficacy and safety.

These analyses include one interim analysis and one final analysis. In the analyses described in this SAP, the treatment arms will be referred to as Cohort 1, Cohort 2, Cohort 3, and Cohort 4. The purpose of the SAP is to ensure the credibility of the study findings by pre-specifying the statistical approaches to the analysis of study data prior to database lock and any data analysis had begun for the interim/final analysis. This SAP will be finalized and signed prior to the clinical database lock for the interim/final analysis. All statistical analyses detailed in this SAP will be conducted using *SAS*[®] Version 9.2 or higher.

3. STUDY OBJECTIVES

3.1. Primary Objective

The primary objectives of the study are to assess the safety and determine the maximum tolerated dose (MTD) of PDA-002 administered intramuscularly (IM) in subjects with peripheral arterial disease (PAD) and DFU.

3.2. Secondary Objectives

The secondary objective is to explore potential clinical efficacy by assessing changes in the ankle-brachial index (ABI) and/or toe brachial index (TBI). Additional assessments will include evaluating changes in Rutherford Criteria; number, extent and size of ulcers; leg rest pain score using a visual analogue scale (VAS); incidence of hospitalization (all cause); overall survival at 24 months; and the time to first occurrence of major amputation (above the ankle) of treated leg, all-cause mortality, doubling of index ulcer total surface area from baseline, de novo gangrene of treated leg reopening of closed ulcer, index ulcer reduction by 50%, or time to ulcer healing.

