### **Overview of Efficacy Assessments**

The following efficacy assessments will be performed:

1. ABI and TBI will be calculated by dividing the systolic blood pressure at the ankle or toe by the systolic blood pressures (Doppler technique) in the arm. ABI and TBI will be measured during Screening, on Study Days 1 and 8 prior to administration of IP and on Study Days 15 and 29 and Months 3, 6, 9, 12, and 24.
2. The number, extent, and size of ulcers (summation of the products of the long x short axis for all ulcers measured in centimeters squared, plus ulcer depth) will be evaluated and the ulcers photographed during Screening and again on Study Days 1, 8, 15, and 29 and Months 3, 6, 9, 12, and 24.
3. Time to first occurrence of major amputation (above the ankle) of treated leg, doubling of ulcer total surface area from baseline, and de novo gangrene.
4. Wagner Grading Scale assessed during Screening and on Study Days 1, 8, 15, and 29 and Months 3, 6, 9, 12, and 24.

5. Rutherford Criteria assessed during Screening and on Study Days 1, 8, 15 and 29 and Months 3, 6, 9, 12, and 24.
6. Leg rest pain score - VAS graded from 0 (pain free) to Grade 10 (maximum pain) during Screening, on Study Days 1 and 8 prior to administration of PDA-002 and on Study Days 15 and 29 and Months 3, 6, 9, 12, and 24.
7. Overall survival at 24 months (time from PDA-002 administration to any cause of death, subjects still alive will be censored at the date of last follow-up).
8. Incidence of hospitalization (all cause).

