### **2.2. Secondary Objectives**

The secondary objective is to explore potential clinical efficacy by assessing changes in the ankle-brachial index (ABI) and/or toe brachial index (TBI). Additional assessments will include evaluating changes in Rutherford Criteria; number, extent and size of ulcers; leg rest pain score using a visual analogue scale (VAS); incidence of hospitalization (all cause); overall survival at 24 months; and the time to first occurrence of major amputation (above the ankle) of treated leg, all-cause mortality, doubling of ulcer total surface area from baseline or de novo gangrene.

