### 3.2. Secondary Endpoints

The secondary endpoints are to explore clinical efficacy and include:

1. ABI and TBI will be calculated by dividing the systolic blood pressure at the ankle or toe by the systolic blood pressures (Doppler technique) in the arm. ABI and TBI will be measured during Screening, on Study Days 1 and 8 prior to administration of IP and on Study Days 15 and 29 and Months 3, 6, 9, 12 and 24.
2. The number, extent, and size of ulcers (summation of the products of the long x short axis for all ulcers measured in centimeters squared, plus ulcer depth) will be evaluated and photographs of ulcers taken during Screening and again on Study Days 1, 8, 15, and 29 and Months 3, 6, 9, 12, and 24 ([Appendix E](#), [Appendix F](#)).
3. Time to major amputation (above the ankle) of treated leg, doubling of ulcer total surface area from baseline and de novo gangrene.
4. Wagner Grading Scale ([Appendix A](#)) assessed during Screening and on Study Days 1, 8, 15, and 29 and Months 3, 6, 9, 12, and 24.
5. Rutherford Criteria ([Appendix B](#)) assessed during Screening and on Study Days 1, 8, 15, and 29 and Months 3, 6, 9, 12, and 24.
6. Leg rest pain score - visual analogue scale (VAS) ([Appendix D](#)) graded from 0 (pain free) to Grade 10 (maximum pain) during Screening, on Study Days 1 and 8 prior to administration of PDA-002 and on Study Days 15 and 29 and Months 3, 6, 9, 12, and 24.
7. Overall survival at 24 months (time from PDA-002 administration to any cause of death, subjects still alive will be censored at the date of last follow-up).
8. Incidence of hospitalization (all cause).

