### **10.6. Efficacy Analysis**

Efficacy analyses will be conducted using the Efficacy Evaluable (EE) population as defined in Section 10.2. Descriptive statistics will be provided primarily for summaries of efficacy endpoints. No formal statistical comparisons are planned due to the small sample size and the exploratory nature of the study.

Descriptive statistics will also be provided for changes in Rutherford Criteria, number, extent and size of ulcers, ABI, TBI, leg rest pain score (VAS), and incidence of hospitalization.

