4.2.2. Secondary Efficacy Endpoints

The secondary endpoints are to explore clinical efficacy and include:

- 1) ABI and TBI will be calculated by dividing the systolic blood pressure at the ankle or toe by the systolic blood pressures (Doppler technique) in the arm. ABI and TBI will be measured during Screening, on Study Days 1 and 8 prior to administration of IP and on Study Days 15 and 29 and Months 3, 6, 9, 12 and 24.

- 2) The number of ulcers and the size of the index ulcer (length, width, depth and EZ Graph area) will be evaluated and photographs of ulcers taken during Screening and again on Study Days 1, 8, 15, and 29 and Months 3, 6, 9, 12, and 24 (Appendix E, Appendix F of study protocol).
- 3) Time to major amputation (above the ankle) of treated leg, doubling of index ulcer total surface area from baseline, de novo gangrene of treated leg, reopening of closed ulcer, index ulcer reduction by 50%, and time to ulcer healing. Number of ulcers that completely close at 3 months, if they closed at least 50% at one month.
- 4) Extent of ulcers will be examined with the Wagner Grading Scale. The Wagner Grading Scale (Section 16.3) is assessed during Screening and on Study Days 1, 8, 15, and 29 and Months 3, 6, 9, 12, and 24.
- 5) Rutherford Criteria (Section 16.4) assessed during Screening and on Study Days 1, 8, 15, and 29 and Months 3, 6, 9, 12, and 24.
- 6) Leg rest pain score - visual analogue scale (VAS) (Appendix D of study protocol) graded from 0 (pain free) to Grade 10 (maximum pain) during Screening, on Study Days 1 and 8 prior to administration of PDA-002 and on Study Days 15 and 29 and Months 3, 6, 9, 12, and 24.
- 7) Overall survival at 24 months (time from PDA-002 administration to any cause of death, subjects still alive will be censored at the date of last follow-up).
- 8) Incidence of hospitalization (all cause).

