10.3.3. Secondary Endpoint 3 – Time to Major Amputation

Descriptive statistics for time to major amputation (above the ankle) of treated leg, time to doubling of index ulcer total surface area from baseline in treated leg, de novo gangrene in treated leg, time to reopening of closed ulcer, time to index ulcer total surface area reduction from baseline by 50%, and time to ulcer healing will be presented by cohort.

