10.3.7. Secondary Endpoint 7 – Overall Survival

Overall survival at 24 months (time from PDA-002 administration to any cause of death) will be summarized using descriptive statistics by cohort. Subjects still alive will be censored at the date of last follow-up.

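### The first-occurrence composite named in the objectives is defined inconsistently and has no analysis; survival and limb events are summarised on the Efficacy Evaluable set with no stated time-to-event method

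*SAP*

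**What the plan says.** **Protocol, objectives.** Section 2.2 lists, among the additional assessments, time to first occurrence of major amputation of the treated leg, "all-cause mortality, doubling of ulcer total surface area from baseline or de novo gangrene". The synopsis objectives and Section 4.1 name the same four events, and Section 4.1 refers the reader to Section 3 for them.

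**Protocol, endpoints.** The synopsis (Overview of Efficacy Assessments, item 3) has "Time to first occurrence of major amputation (above the ankle) of treated leg, doubling of ulcer total surface area from baseline, and de novo gangrene", without death. Section 3.2, item 3, has "Time to major amputation (above the ankle) of treated leg, doubling of ulcer total surface area from baseline and de novo gangrene", with neither death nor a first-occurrence rule. Section 10.6 names no time-to-event analysis; its specific list begins "Descriptive statistics will also be provided for changes in Rutherford Criteria, number, extent and size of ulcers, ABI, TBI, leg rest pain score (VAS" and ends with hospitalization.

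**SAP.** Section 3.2 keeps the first-occurrence wording and all-cause mortality, and extends the same list with "de novo gangrene of treated leg reopening of closed ulcer, index ulcer reduction by 50%, or time to ulcer healing". Section 4.2.2, item 3, begins "Time to major amputation (above the ankle) of treated leg, doubling of index ulcer total surface area from baseline, de novo gangrene of treated leg" and goes on to reopening, 50% reduction and healing, with no death and no first occurrence. Section 10.3.3 promises "Descriptive statistics for time to major amputation (above the ankle) of treated leg, time to doubling of index ulcer total surface area from baseline", followed by the remaining components, by cohort. Overall survival (Section 10.3.7) is also given descriptive statistics, with the rule "Subjects still alive will be censored at the date of last follow-up". Section 10 places all efficacy evaluations on the Efficacy Evaluable (EE) set. Section 5.2.1 defines that set as treated subjects with a baseline and at least one post-baseline efficacy assessment.

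**The concern.** A reader who starts from the objectives expects one result: how long subjects remain free of limb failure or death. Nobody programming from the SAP would produce it, and two people trying to would disagree on whether death counts. SAP 3.2 taken literally makes this worse, because a healed ulcer and an amputation would both end the clock, and the result would have no direction of benefit.

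The component times have a separate problem. Death prevents every later limb event, and major amputation prevents healing of an ulcer on that leg. Subjects without an event are censored at different times. This matters most at the interim analysis, which runs when the last subject reaches Month 3: cohorts enrol in sequence, so earlier cohorts have longer follow-up by then. Without a stated method, a table of times may describe only the subjects who had events.

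Finally, requiring a post-baseline efficacy assessment makes entry into the survival analysis depend on surviving to that assessment.

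**Working it through.** **1. Definitions side by side**

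| Place | First occurrence? | Death in list? | Healing or 50% reduction in list? |
|---|---|---|---|
| Protocol synopsis objectives, 2.2, 4.1 | yes | yes | no |
| Protocol synopsis, efficacy item 3 | yes | no | no |
| Protocol 3.2, item 3 | no | no | no |
| SAP 3.2 | yes | yes | yes |
| SAP 4.2.2, item 3 | no | no | yes, as further endpoints |
| SAP 10.3.3 | no | no | yes, as separate times |

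The four-event composite appears only in objective or design text, never in an endpoint list or analysis section. SAP Section 14 declares the treated-leg restriction and the added reopening, 50% reduction and healing times. It does not mention the composite.

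**2. The only design figure.** Maximum enrolment is 4 cohorts x 6 subjects = 24, as stated. It does not come from a formal calculation, and there is no power or event figure to reproduce.

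The documents give no event rates. Steps 3 to 5 therefore assume exponential times over 24 months, independent between event types in steps 3 and 4, with risks shown as ranges.

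**3. What including death changes.** Let d be the 24-month death risk and h the limb-event risk, each in the absence of the other.
- Composite = 1 - (1-d)(1-h).
- Limb event first = composite x ln(1-h) / [ln(1-h) + ln(1-d)].
- d = 10%, h = 40%: composite 0.46, limb event first 0.38, difference 1.9 of 24 subjects.
- d = 30%, h = 20%: composite 0.44, limb event first 0.17, difference 6.5 of 24 subjects.

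Over d = 10-30% and h = 20-40%, the difference stays between these two values.

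**4. SAP 3.2 taken literally.** Let b be the 24-month chance of 50% ulcer reduction. The share of first occurrences that are benefits is ln(1-b) / [ln(1-b) + ln(1-h)].
- h = 40%, b = 40%: 50%.
- h = 20%, b = 80%: 88%.

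**5. If only observed event times were averaged.** With event risk p by Month 24, the rate is λ = -ln(1-p)/24. The mean among events is 1/λ - 24(1-p)/p, and the 24-month restricted mean is p/λ.
- For p = 50%: 1/λ = 34.62, so the mean among events is 34.62 - 24 = 10.6 months, while the true median is 24 months.

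| p | Restricted mean (months) | Mean among events (months) | P(no event in 6) | P(at least 3 events in 6) |
|---|---|---|---|---|
| 10% | 22.8 | 11.8 | 0.53 | 0.02 |
| 20% | 21.5 | 11.6 | 0.26 | 0.10 |
| 40% | 18.8 | 11.0 | 0.05 | 0.46 |
| 60% | 15.7 | 10.2 | <0.01 | 0.82 |

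The event-only mean moves by 1.6 months (11.8 - 10.2) while the restricted mean moves by 7.1 (22.8 - 15.7). The last column is the chance that a Kaplan-Meier median is reached in a cohort of 6 with complete follow-up.

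**6. Who the EE set can lose.** Efficacy is assessed on Day 8 and, under Protocol 6.3, at early termination. Exclusions are therefore mainly treated subjects who die or are lost before any such assessment, and these are probably few.

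**The case against.** Several stronger readings are tempting, and the other side is right to resist them.

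- **That the SAP drops death.** It does not. Overall survival is secondary endpoint 7, with its own section and censoring rule, and deaths are listed by subject under safety. Death is missing only from endpoint 3.
- **That the SAP silently removed a protocol analysis.** SAP 4.2.2 follows Protocol 3.2, which already lacked death and first occurrence, and Protocol 10.6 never planned the composite. SAP Section 14 covers changes to the protocol's statistical section, so its silence is not concealment. The conflict starts inside the protocol.
- **That healed and failed subjects will be counted together.** SAP 4.2.2, 10.3.3 and 14 treat the healing times separately, and the SAP 3.2 sentence does not parse as a composite.
- **That the secondary objective goes unanswered.** The lead secondary objective is change in ABI and/or TBI, which is analysed. The composite is one of the additional assessments, and each of its parts is summarised.
- **That observed event times will simply be averaged.** Descriptive statistics can include Kaplan-Meier summaries, and SAP 5.1 and 16.1 are redacted. Step 5 illustrates one possible reading, not a stated method.

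It is also fair that cohorts of 3 to 6 yield little from curves. What remains is that the composite has no analysis, its definitions disagree, SAP 3.2 is wrong as written, and the visible text names no time-to-event method for endpoint 3 or for survival.

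**Conclusion.** The point holds as a gap in specification. The documents disagree on what the composite is, and no visible section analyses it. Endpoint 3 has no visible censoring or competing-event rule, and overall survival has a censoring rule but no named method that uses it. Survival and amputation are run on a set that could exclude an early death or loss.

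The consequence is limited. The endpoint is secondary, descriptive and untested, and the MTD does not depend on it. Whether death counts could change the composite by about 2 to 6.5 of 24 subjects, under the assumed risks in step 3; those deaths would still appear in overall survival or the safety listings. The contrast between 10.6 and 24 months rests on assumed exponential times, an assumed 50% event risk and an assumed method. The 50-88% share of benefits describes a literal reading of SAP 3.2 that the rest of the SAP does not follow. The EE effect is probably small, but it acts on the outcome being measured. The change is worth making because it is cheap.

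**What to change.** 1. Reconcile the Protocol synopsis (objectives and efficacy item 3), Protocol 2.2, 3.2 and 4.1, and SAP 3.2, 4.2.2 and 10.3.3. Define one first-occurrence composite of harms only, and state whether death is included and why.
2. List 50% reduction, healing and reopening as separate endpoints, outside the first-occurrence sentence.
3. In SAP 10.3.3 and 10.3.7, use the Safety population. State the start date (there are two administrations, so say which) and the censoring rule for each endpoint.
4. Report the composite and overall survival by Kaplan-Meier with numbers at risk, by cohort and pooled.
5. Report amputation, gangrene, doubling and healing as event counts with cumulative incidence. Treat death as a competing event and, for healing, major amputation as well.
6. Record the change in SAP Section 14.

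The cost is document wording and standard SAS procedures; no new data are needed. The downside is coarse cohort curves. With 6 subjects and a 20% event risk, the chance of reaching a median is about 0.10, so pooled results and a listing of subject-level times will carry most of the information.
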